DESCRIPTION OF STUDY

Principal Investigator: [name], PhD
Title of the Study: CCRC: "The independent effects of level of kidney function and body composition on establishing HDL cholesterol levels" (220939-7)

PURPOSE AND PROCEDURES:

1. Describe the study format and whether it is single or multi-center; industry-sponsored or investigator initiated; and the funding source.

This is a single center cross sectional analysis of body composition and lipoprotein level and structure among patients with graded levels of renal failure in comparison to control subjects. This is not a treatment or outcome trial.

2. Briefly describe the specific aims of the study, research methods and procedures.

To establish the relationship between HDL cholesterol and both body composition and insulin resistance measured as HOMA among a cohort of non diabetic non proteinuric patients with advanced CKD, (stage IIIb, Stage IV and stage V) compared to non diabetic subjects having normal kidney function (eGFR \geq 80 ml/min)

3. Address if therapeutically removed tissue will be collected, what types, and for what purposes.

N/A

4. Specify the nature, frequency and duration of tests, if any.

There is a potential for blood to be drawn two times. In patients who are under immediate care with recorded fasting blood sugar values in the non diabetic range (less than 120 mg/dL) obtained in the past 6 months, no blood samples will be obtained for screening and patients will be studied or excluded based upon laboratory values in either the UC Davis or DCI. The creatinine available in the medical record will also be used to establish the level of renal function. In patients in whom no recent evidence is available to exclude diabetes and for the valuation of baseline renal function, approximately 5 cc of blood will be obtained to measure a fasting blood sugar and serum creatinine. Patients with fasting blood sugar values equal to or greater than 120 mg/dL will be excluded. Dialysis patients have blood drawn at least monthly making only a single sample necessary for these patients. Subjects who are not on dialysis, i.e. normal control subjects and patients having chronic kidney disease may require two blood samples - one 5 ml sample (1 teaspoon) and one 45 ml (3 tablespoon) sample obtained.

5. If blood samples will be collected, identify in what manner and the maximum amount that will be collected over any 6 week period (if subjects are co-enrolled in other research studies, the volume of blood from the other study should also be included):

venipuncture venous catheter arterial puncture arterial catheter cutaneous

6. Any additional procedures (noninvasive) involved in this study activity must be described.

Mass, lean tissue mass, and bone mineral content, using a Hologic Discovery W bone densitometer (Hologic, Bedford, Massachusetts) in accordance with standardized procedures recommended by the manufacturer. DXA measurements will be performed with the patient in the supine position, dressed in light clothing, and wearing no metal objects. Total body scanning time will be approximately 11 min, and the total x-ray radiation received by each patient will be approximately 0.4 mrem.

Whole body bioimpedance spectroscopy (BIS) measurements will be performed using two different devices: 1.) an ImpediMed (ImpediMed Limited., San Diego, CA); 2) the Xitron in all patients while patients are in the supine position at the CCRC. Dialysis patients will be studied on a non dialysis day. The areas for electrode attachment will be cleaned with alcohol. Two injecting electrodes for applying alternating current will be placed on

the ipsilateral dorsal surfaces of the hand (11) and the foot (12), and two sensing electrodes will be placed on the wrist and the ankle. Current is injected for a spectrum of 50 frequencies ranging from 5 kHz to 1 MHz. A computer is used for data acquisition, data storage, and data analysis. Extracellular resistance will be determined as the limit of resistance at zero frequency by fitting the impedance data using the modified Cole-Cole model with software supplied with the impedance device. The rationale for two BIS devices is the Xitron was used to develop our equations for body composition and we want to make certain the results of the two instruments are not significantly different in both the control and dialysis patient populations. Our standards are all with the Xitron, so we need to verify that we are getting the same results. Xitrons are no longer produced and are unavailable for purchase. We want to verify the equations we generated relating body composition performed with the Xitron work for the Impedimed. The Xitron is more difficult to use since the computer and measurement instrument are separate devices. The Impedimed is easier to use and portable. but for the patient they are identical.

Blood will be drawn at the CCRC at the same visit in which DEXA and BIS measurements are made to avoid multiple trips to the CCRC. The exception is for dialysis patients. In their case, to avoid unnecessary venipuncture, blood will be drawn immediately prior to a mid-week dialysis session. Heparin dose of 50U/kg will be given to these patients. For dialysis on this day, no heparin maintenance will be given thus eliminating additional risk.

Those subjects not receiving dialysis will receive an injection of heparin (50 U/kg) during the course of having blood drawn and are thus subjected to a small risk of increased bleeding for the 4-6 hour period following the injection. No additional venipuncture will be performed to administer the heparin.

7. If the study involves incomplete disclosure, provide the rationale.

N/A

8. If this activity will be utilizing existing data, specify the source and how the data will be retrieved, reviewed, coded and stored.

Urine Protein, Creatinine, medical history. In order to recruit subject with chronic kidney disease (CKD), initially ask or review medical record to check for inclusion criteria (no labs will be done at this time). If eligible then he/she will be enrolled. This permission will be obtained by consent.

9. Address the location and duration of the study including follow-up period.

The study will take about an hour and will be conducted at the CCRC located in the Cypress Building, [name].

10. Clarify how you plan to monitor data to ensure subject safety.

Labs with critical values are reported to [name] directly.

11. Address whether you have the appropriate resources (study personnel and facilities) to conduct this study.

We have requested funding for a half time clinical coordinator who will be dedicated to this study for 2 years. The PI and the co PI will each devote 5% effort to recruitment, safety monitoring and data analysis.

12. Describe the role of each key member of your study personnel.

- [name] --Physician/PI: write/collaborate on manuscript from data collected and oversees study
- Physician/Co-PI: consent/collaborate on manuscript from data collected and oversees study
- CRC/Lab Tech: enroll, consent, collect specimen(s) as well as run assays on specimen(s).

SUBJECT SELECTION:

1. Identify the subject population.

The study population will consist of 20 prevalent hemodialysis patients, 20 patients having an estimated glomerular filtration rate (eGFR) between 15 and 29 and 20 patients having an eGFR between 30 and 45. Thirty subjects having normal renal function (eGFR \geq 80 ml/min) will be studied. Patients must be non diabetic (FBS \leq 120 mg/dl, not taking oral contraceptives or hormone replacement therapy, not on steroids, not on HIV treatment regimen, not have a functioning renal transplant and not taking a lipid lowering agent at the time of the research study.

2. Address how subjects will be recruited: direct person to person solicitation, by telephone, letter, advertisement, press release, notices, other. Provide the text.

See attached recruitment flyer(s).

3. State from where subjects will be recruited, when and how many.

Patients will be recruited from the UC Davis chronic kidney disease clinics (Stage IIIb and Stage IV CKD, from the dialysis patient population at our 4 DCI dialysis clinics (University, Southgate, Madison, and Rancho Cordova, and if necessary from the DaVita dialysis units which we are affiliated. Normal subjects will be recruited through the and by posting notices at University of California Davis, and on the bulletin boards at the UC Davis main campus.

Will be recruiting from outside of UC Davis and DCI using IRB approved methods.

4. Specify the age of the research subjects.

18-75 years old.

5. List all criteria for including and excluding subjects.

Inclusion: Subjects will be recruited who are between 18 and 75.

Inclusion criteria:

- Men and women - ages 18-75
- Self report of stable body weight during the past six months
- BMI 18-40 kg/m²
- Hemodialysis dependent for at least 3 months (prevalent ESRD cohort)
- eGFR \geq 15 \leq 44 ml/min (CKD cohort)
- eGFR \geq 80 ml/min (Control cohort)

Exclusion Criteria:

- Diabetes Mellitus (American Diabetes Association definition: fasting glucose $>$ 120 mg/dl)
- Evidence of liver-hepatitis B, or thyroid disorders
- HIV by medical history (HIV test will not be performed)
- Renal transplant recipient
- Oral contraceptive, hormone replacement therapy
- Systemic use of systemic or inhaled corticosteroids in the past month
- Contraindication to systemic anticoagulation (heparin administration is necessary to measure levels of LPL, HL).
- Hemoglobin $<$ 8.5 g/dl (anemia)
- Current, within 2 months use of any hypolipidemic or anti-diabetic agents.
- Any other condition that, in the opinion of the investigators, would put the subject at risk
- Patients treated with a fibric acid derivative or niacin in the past 4 weeks.
- Urinary protein excretion of greater than 0.5 grams per day.

Patients will be screened by collection of serum for fasting blood sugar, creatinine, and measurement of urine

6. If women and minorities are excluded, provide rationale for such exclusion.

N/A

7. Attach the translated documents for subjects whose primary language is not English.

N/A

SPECIAL/VULNERABLE POPULATION (if applicable):

Surrogate consent for participation in a research study should be employed only to the extent that it is consistent with the intent of the Common Rule (45 CFR 46, Subpart A) and all other federal and state laws and regulations pertaining to protecting human subjects participating in research. Carefully review the IRB Policy on *Surrogate Consent For Research* for compliance with all applicable laws, regulations, and conditions of this policy. Investigators are reminded that use of surrogate consent shall apply on a case-by-case basis within the protocol.

1. Identify the vulnerable population: ___ children, ___ mentally handicapped, ___ pregnant women, ___ fetuses, ___ prisoners, ___ cognitive impairment, ___ life-threatening disease, or ___ social or ___ economically disadvantaged. Address what additional safeguards you will put into place to protect the rights and welfare of this population.

N/A

2. If you are seeking IRB approval for use of surrogate consent, justify the appropriateness of such use and describe your specific plan for the assessment of the decision-making capacity of the subject(s).

N/A

RISKS:

1. Address whether there is a possibility of physical, psychological, social or legal injury from participation in this study and assess the likelihood and seriousness of those risks.

Hyperlipidemia: During recruitment/screening, it may be determined that a potential subject qualifies for lipid therapy under NCEP guidelines. Subjects identified with existing hyperlipidemia will be informed of the small, but potential risk of delaying treatment during the study period. They will be informed they have the option to not participate in the study and begin the lipid-lowering therapy recommended by their physician.

Blood Collection: There is potential for bruises at the site blood collection procedures. The volume of blood collected during all procedures will be within guidelines for minimal risk blood draw.

There is a chance of bruising, or very rarely, an infection at the site where blood will be taken. Proper aseptic blood collection techniques will be used to minimize these risks.

Heparin: Patients will each receive a single dose of heparin. This imparts a small risk of hemorrhage.

Heparin will be administered to non dialysis patients while the patients are in the CCRC minimizing the risk of trauma during the period of systemic anticoagulation. There is a small risk of bleeding from Heparin.

Patients who are on dialysis receive heparin as a component of dialysis treatment. Blood will be drawn prior to dialysis initiation, but no additional needle stick or heparin administration will be required of these patients.

DEXA: Subjects will be exposed to a very small amount of x-ray radiation (0.4 mrem) for each DEXA procedure. There are no known health risks associated with radiation exposure levels this low.

2. If the methods of research create potential risks, describe other methods, if any, that were considered and why they will not be used.

The risks involved are minimal. It is not possible to measure the levels of the relevant enzymes without heparin administration. The exposure to ionizing radiation is approximately equal to that exposure received by dental X-rays. The outcome of interest is dyslipidemia. It is not possible to explore this in the at risk population without withholding lipid lowering drugs for approximately 60 days if the patients are already being treated.

3. Identify your plan for protecting subject privacy and confidentiality.

All relevant laboratory and clinical data will be abstracted by the PI and the study coordinator and coded. The linkage information will either be kept in a locked drawer in the Genome facility at UC Davis or stored on a computer not linked to the internet at that facility. All other data will be coded and individual patient identifiers will be removed. At the conclusion of data acquisition all linking material will be shredded.

4. Explain your plan for reporting adverse and serious adverse events to the IRB.

All serious AEs will be reported to the IRB within 24 hours by either the PI or the co-PI if the PI is not on campus.

5. If the study involves the use of placebo, justify why this is appropriate.

N/A

BENEFITS:

1. Address if there is a benefit to individual subjects or to the particular group or class.

No direct benefit will accrue to the individual participants other than discovering dyslipidemia in patients who may not already be aware of this risk factor. In this case patients will be directed to a treating physician. Elucidation of the mechanism of reduced HDL in patients having CKD may ultimately lead to specific treatment for this disorder, a risk factor for further loss of renal function and for vascular disease in this population.

2. Address if there is no direct benefit to the subject.

The risk is small. The principal benefit is that of establishment of a lipid disorder in individual patients. Ultimately we hope to be able to evaluate existing agents for increasing HDL in patients having CKD to affect outcome, or to design new therapy based upon our findings.

RISK-BENEFIT RATIO:

1. Address whether the risks to subjects are reasonable in relation to the benefits (note: do not state that the benefits outweigh the risks. Rather, construct a summary assessment of the relative risks (physical, psychological, economical, and legal) to participants versus the potential benefits to participants and society).

N/A

COSTS/COMPENSATION TO SUBJECTS:

1. If the study involves the possibility of added expenses to the subject or to a third party, such as an insurer (e.g., longer hospitalization, extra laboratory tests, travel) address the magnitude of those expenses and how this is justified.

N/A

2. Describe the amount and type of compensation that will be paid to subjects and how that compensation will be staged/pro-rated.

Subjects will be compensated \$50.00 once they have completed participation in the study.

DISCLOSURE OF PERSONAL AND FINANCIAL INTEREST:

1. Disclose any personal and financial interest in the research as well as the extent of personal and financial interest in the sponsor.

None

WAIVER OF INFORMED CONSENT (if applicable): N/A

If you are requesting waiver or alteration of informed consent, you are required by federal regulations to justify the following four points, for review by the IRB:

1. The research involves no more than minimal risk to the subjects.
2. The waiver or alteration will not adversely affect the rights and welfare of the subjects.
3. The research could not practicably be carried out without the waiver or alteration.
4. Whenever appropriate, the subjects will be provided with additional pertinent information after participation.

Waiver for use of Protected Health Information for Recruitment The use or disclosure of PHI involve no more than a minimal risk to the privacy of the individual based on at least the presence of the following.

Only authorized persons will be given access to the identifiers and/or data-storage devices will be encrypted and password protected; identifiers maintained in paper format will be kept in a locked area accessible by only research staff who require access.

I will destroy the identifiers at the earliest opportunity consistent with the conduct of the research unless there is a health or research justification for retaining the identifiers or as otherwise required by law.

Protected health information from this research will not be reused or disclosed to another person or entity, except as required by law, for authorized oversight of the research study, or other research for which the use or disclosure of PHI.

I will use Quick Disclosure Activity in EMR to track all medical records accessed as defined by P&P 2446.

Elements of Health Information *

Please list the specific elements of health information for which you are requesting the wavier. t

Serum creatinine, history of diabetes, use of lipid lowering medication, presence of proteinuria greater than 500 mg per day.

Reasons for the Waiver *

What specific information will this waiver cover and why do you need this wavier to be able to conduct the research?

To avoid unnecessary contact between research staff and patients who are not eligible to participate in the study. If patients are eligible they will be approached and asked to participate and if they are willing they will be asked to provide consent to enroll in the study.

TOTAL NUMBER OF COPIES REQUIRED FOR SUBMISSION TO THE IRB ADMINISTRATION:

Original plus 1 copy

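### A non-significant Xitron–ImpediMed difference would not show that the devices agree; report the mean difference and limits of agreement

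*Protocol*

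**What the plan says.** Item 6 of Purpose and Procedures in the protocol describes whole-body bioimpedance spectroscopy on an ImpediMed and on "the Xitron in all patients while patients are in the supine position at the CCRC". It then explains why there are two: the group's existing body composition equations come from the Xitron. The standard for comparing the instruments is worded as follows: "we want to make certain the results of the two instruments are not significantly different in both the control and dialysis patient populations". The goal is put in two further ways: "Our standards are all with the Xitron, so we need to verify that we are getting the same results" and "We want to verify the equations we generated relating body composition performed with the Xitron work for the Impedimed". The practical motive is that "Xitrons are no longer produced and are unavailable for purchase".

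The protocol names no test, significance level, acceptable difference or agreement statistic for this check. The available Statistical Plan in the SAP covers only a linear regression of LCAT, CETP and LPL on eGFR and does not mention the devices. One part of the SAP was not available for this review, so nothing is claimed about the SAP as a whole.

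**The concern.** The goal is interchangeability: a reading from one device should be able to stand in for a reading from the other in an existing equation. The only wording that resembles a criterion is absence of a significant difference, which answers another question.

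- Failing to reject a zero mean difference in a small group is weak evidence that the difference is small.
- A test of the mean says nothing about how far the devices differ in a single patient, which matters when an equation is applied patient by patient.
- The criterion can also err the other way, rejecting a trivial but consistent offset.

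At stake is whether the group could conclude that its equations transfer to the ImpediMed when this has not been shown. The documents do not show any effect on the HDL analysis.

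**Working it through.** The plan gives no figure for this check, so there is none to reproduce. The following illustrates what the wording would imply if used as a test.

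**Inputs**
- Dialysis n = 20 and controls n = 30: planned numbers, protocol, Subject Selection, item 1.
- Assumed, because the documents are silent: paired t-test, two-sided 5%, one reading per device per patient, normally distributed differences. The unit is the SD of the between-device differences.

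**Largest observed mean difference that still passes**, t(0.975, n−1)/√n:
- n = 20: 2.093/√20 = 0.468 SD
- n = 30: 2.045/√30 = 0.373 SD

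At that value the 95% CI runs from zero to twice the figure, that is to 0.936 SD and 0.747 SD.

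**Chance that a true bias is missed** (noncentral t with noncentrality bias × √n). The last column assumes the same bias in two independent groups and multiplies the two probabilities.

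| True bias | n = 20 | n = 30 | Both groups pass |
|---|---|---|---|
| 0.3 SD | 0.753 | 0.645 | 0.49 |
| 0.5 SD | 0.435 | 0.246 | 0.11 |

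If a 0.5 SD bias existed in dialysis patients only, both groups would pass with probability 0.435 × 0.95 = 0.41. The bias detectable with 80% power is 0.66 SD (n = 20) or 0.53 SD (n = 30).

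**Individual scatter.** With zero mean bias each group passes 95% of the time whatever the SD. Simulation gave 0.949 to 0.951 for SDs of 1, 10 and 100 units, while the limits of agreement (±1.96 SD) widened from ±1.96 to ±19.6 to ±196 units. The test result does not respond to this.

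**Opposite error.** A bias of 1 SD is significant 98.9% of the time at n = 20 and over 99.9% at n = 30, even if that SD is negligible in measurement units.

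**Precision of the alternative.** The 95% CI half-width of the mean difference is 0.468 SD (n = 20) or 0.373 SD (n = 30). For each limit of agreement it is t × √(1/n + 1.96²/(2(n−1))):
- n = 20: 2.093 × √(0.0500 + 0.1011) = 0.814 SD
- n = 30: 2.045 × √(0.0333 + 0.0662) = 0.645 SD

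**The case against.** The phrase comes from an ethics-form answer explaining why patients are measured twice, not from an analysis section. It may simply mean not materially different, and the neighbouring sentences speak of agreement. That is fair, and it is why the point is conditional. It does not supply an agreement analysis, and none appears elsewhere in the available text.

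The silence of the SAP is weak evidence, because part of it was unavailable and the rest is a short retrospective note on enzymes and lipids. This also stands; the point rests on the protocol wording.

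The protocol wants no difference in both populations, so per-group miss rates overstate the risk when the bias is common to both: at 0.5 SD the joint rate is about 11%. This is correct and is shown above. It weakens that example but not the 0.3 SD case (49%), a bias confined to one group, or the blindness to scatter.

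Finally, limits of agreement without a pre-stated acceptable difference are descriptive and leave the question of transfer to judgement. That is true. They still show the size of the disagreement, which a non-significant p-value does not. The documents do not confirm how many paired readings exist.

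**Conclusion.** The point holds in its conditional form: used as the standard, a non-significant difference would not show that the ImpediMed can replace the Xitron. With the planned 20 and 30 patients, observed mean differences up to 0.47 and 0.37 SD would pass, and individual disagreement of any size would go unexamined. These figures rest on the assumed paired t-test at 5% and one reading per device. Since no SD is given, the biases could be trivial or important in ohms or kilograms. The check is ancillary to the study's aims and priority is low.

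**What to change.** Replace the criterion with an agreement analysis, separately for controls and dialysis patients:

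- Report the mean device difference with its 95% CI, and the 95% limits of agreement with their CIs. Do this for the resistances (the protocol states that "Extracellular resistance will be determined as the limit of resistance at zero frequency") and for the body composition values the equations predict.
- Check whether the difference changes with the size of the measurement.
- Where the equations predict something DXA also measures (item 6 lists "Mass, lean tissue mass, and bone mineral content, using a Hologic Discovery W bone densitometer"), compare each device's prediction with DXA. The documents do not say what the equations predict, so this applies only if there is overlap.
- State that a non-significant test will not be read as agreement, and present the results as estimates, not as a pass/fail equivalence verdict. If the group can state an acceptable difference before seeing the data, that would make the limits easier to interpret.

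The cost is a sentence of text and a short analysis. Both devices are already planned in all patients, so no new measurement is needed, and the estimates can be reported from any paired readings already collected. The drawback is the limited precision: about ±0.81 SD (n = 20) or ±0.65 SD (n = 30) on each limit.

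### Are the LPL and HL samples in dialysis patients taken before heparin, and so unusable by the protocol's own account?

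*Protocol*

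**What the plan says.** The assay requirement appears twice in the Protocol. Under Subject Selection, item 5, the exclusion for contraindicated anticoagulation is justified because "heparin administration is necessary to measure levels of LPL, HL". Risks, item 2, says "It is not possible to measure the levels of the relevant enzymes without heparin administration".

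For subjects not on dialysis, Purpose and Procedures, item 6, ties the two events together: they "will receive an injection of heparin (50 U/kg) during the course of having blood drawn".

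For dialysis patients there are two descriptions:

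- Purpose and Procedures, item 6: "blood will be drawn immediately prior to a mid-week dialysis session. Heparin dose of 50U/kg will be given to these patients". The same paragraph withholds maintenance heparin for that session.
- Risks, item 1: "Patients will each receive a single dose of heparin", then "Patients who are on dialysis receive heparin as a component of dialysis treatment", then "Blood will be drawn prior to dialysis initiation, but no additional needle stick or heparin administration will be required of these patients".

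Purpose and Procedures, item 4, adds "Dialysis patients have blood drawn at least monthly making only a single sample necessary for these patients".

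The SAP lists LPL with LCAT and CETP as enzymes to be regressed on residual eGFR. It reports that the regression was not carried out, because CKD3b and CKD4 patients who met the criteria and were willing could not be recruited.

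**The concern.** For non-dialysis subjects the injection happens within the blood draw. For dialysis patients that link is missing: the draw is placed before the session, the heparin is described as part of dialysis, and no further administration is said to be needed. Taken at face value, blood comes first and heparin second. By the protocol's own account such a sample could not give LPL or HL.

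If that happened, LPL and HL would have been sampled on different terms in dialysis patients and in everyone else. A difference between the groups could then reflect sampling and not kidney function. The same would hold for the slope of LPL on eGFR if dialysis patients entered that regression, which the SAP does not say. LPL is the enzyme the SAP links to triglycerides, and dialysis patients are the group whose lipid pattern opens its rationale, so the question was worth asking.

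**Working it through.** The plan gives no figure to reproduce. The check is a comparison of the passages, followed by a simple count.

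**1. Does the Risks section establish a sample before heparin?** It supplies three statements: heparin belongs to the dialysis treatment, blood is drawn before dialysis starts, and no extra heparin is needed. A sample before heparin follows only with a fourth: that heparin is given at or after the start of dialysis. No section says so. The passage also serves to describe risk. Its point is that these patients face no bleeding exposure beyond what dialysis already brings. It does not set out a sampling sequence.

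**2. What does the procedures section add?** Purpose and Procedures, item 6, states 50 U/kg for dialysis patients and 50 U/kg for the others. It places the dialysis dose in the sentence directly after the draw and removes maintenance heparin that day. A dose matched across cohorts, with the usual maintenance withheld, looks like a dose given for the study in place of routine heparin. The single dose per patient in Risks, item 1, agrees. If the sample were taken before heparin, the matched dose would serve no purpose for the assay.

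**3. Does the single sample count against this?** No. Item 4 opens by allowing for two draws, and for non-dialysis subjects these are a 5 ml sample and a 45 ml sample. Dialysis patients can skip the screening draw because they have routine laboratory results. The count is of draw occasions. Non-dialysis subjects also have a single 45 ml study sample, with heparin given during it, so one sample does not rule out blood taken after heparin.

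**4. How much data is in question?** Planned total: 20 + 20 + 20 + 30 = 90 (Subject Selection, item 1).

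| Reading | Dialysis patients losing LPL and HL | Share of planned 90 | Left |
|---|---|---|---|
| Sample before heparin | 20 | 20/90 = 22% | 70 |
| Sample after heparin | 0 | 0% | 90 |

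The SAP says recruitment of the two CKD groups failed but gives no achieved numbers. If neither had enrolled anyone and the other two had filled, the upper figure would be 20/(20 + 30) = 40%. That is an assumption used to show the range.

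**5. Which planned result would move?**

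- The regression of LPL on eGFR is reported as not done.
- The SAP names no contrast of LPL between dialysis patients and controls, and does not mention HL.
- The aim in Purpose and Procedures, item 2, relates HDL cholesterol to body composition and HOMA, and uses neither enzyme.
- HDL, triglycerides, LCAT and CETP are not said individually to need heparin; the protocol names only LPL and HL.

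**The case for a change.** The strongest reply is that a favourable reading is still only a reading. Neither the single dose nor the withheld maintenance states an order. A coordinator who followed the Risks section could draw blood first, give heparin with dialysis, and comply with every sentence. With the CKD groups missing, any LPL result still reported would lean on the dialysis and control groups, where the question bites hardest. The protocol also plans to shred the linking material once data acquisition ends, after which the order used may be hard to trace.

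Part of this stands. The order is unstated for dialysis patients, and the interval from heparin to sample is unstated for every cohort. Anyone who reports LPL or HL in dialysis patients should know how those samples were taken. But that is ordinary checking of data before reporting, and depends on a result that neither document presents. The interval is laboratory-level detail that a short ethics-committee description need not carry. A SAP rule excluding such values would govern a regression already reported as not done and a comparison the SAP never names, so it would alter nothing.

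**Conclusion.** The concern does not hold as a defect in the plan. The Protocol leaves unsaid whether heparin precedes the LPL and HL sample in dialysis patients, and its two descriptions of their heparin are loosely worded. They do not contradict each other unless one adds that heparin is given only once dialysis has started. The more plausible reading has no conflict and loses 0 of 20 dialysis patients. The unfavourable reading would lose all 20, or 22% of the planned 90, for LPL and HL only.

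This judgement rests on two assumptions: that investigators who state the assay requirement twice sampled accordingly, and that no LPL or HL comparison beyond those in the SAP is being reported. The documents cannot confirm what was done at the bedside. If the wording is ever tidied, it is for the investigators to reconcile Purpose and Procedures, item 6, with Risks, item 1; nothing here takes a position on dose or sequence.
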